
Feasibility Substudy: We would like to recruit 15 men, newly joining and currently enrolled in our weight loss trial, via convenience sampling (asked in the calendar order they present for their baseline, 3-month, or 6-month assessment visit in the current clinical trial) to participate in this sub-study. Both arms in our clinical trial receive the same education/instruction about physical activity (i.e. goal of 10,000 steps per day). The men will be invited to participate in this sub-study during their regularly scheduled baseline, 3 month, or 6-month assessment visit with the research nurse at the Northeast

Nebraska Public Health Department in Wayne, NE. Intervention subjects: 40-69 years of age Community advisory board members: 19 or older UNMC Northern Division Student Nurses enrolled in NRSG 413: 19 or older.

Inclusion Criteria

Intervention Subject Inclusion criteria include 1) man age 40-69, 2) reside in the Northeast Nebraska region, 3) BMI between 28 (kg/m²) or higher and weight not greater than 396 pounds (BMI 50 or higher with clinician clearance), 4) smartphone owner with enabled text messaging, 5) speak and read English, 6) have an email account, 7) answer "no" to all questions on the PAR-Q17 health history assessment or are willing to get physician clearance prior to enrolling, 8) willing to share SM logs with investigative team, and 9) attend three assessment visits in Wayne, NE.

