Community advisory board member inclusion criteria includes 1) adult (age 19 or older) who is identified by self or others as a community leader in Cedar, Dixon, Wayne, or Thurston counties, 2) willing to participate in monthly community advisory board meetings for duration of the study, 3) smartphone owner with enabled text messaging. Student nurse inclusion criteria includes 1) adult (age 19 or older) who is enrolled in the UNMC Northern Division's NRSG 413- Population-Centered Care course, 2) willing to participate in a small group discussion about rural community engagement/ community outreach strategies with other students enrolled in NRSG 413 and the principal investigator, [name], during their assigned course time, willing to complete a survey before and after this experience self-assessing their understanding of the public health nurses' role in conducting rural community engagement and outreach.

Substudy: Inclusion criteria would include 1) currently enrolled in the Rural Men's Health Study, and 2) willing to wear on the Actigraph GT9X on your waist for 7 continuous days (except for bathing) and mail back device in the stamped, pre-addressed envelope.

Exclusion Criteria

- 1) have recently lost 5% or more of body weight
- 2) are currently taking medications that cause or are influenced by weight loss (oral steroids, tricyclic antidepressants, lipase inhibitors)
- 3) have used weight loss app in the past to lose weight
- 4) family member from same household is enrolled in this study
- 5) Type I diabetes or Type II diabetes with insulin dependence.

UNMC Northern Division Student Nurses Enrolled in NRSG 413 Exclusion Criteria: none

Substudy exclusion criteria would include a man not currently enrolled in the Rural Men's Health study clinical trial.

Methods

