Following informed consent and completion of baseline visit, eligible participants will be randomized 1:1 to either intervention or comparison group. Participants randomized to the MT+ group will receive *Lose-It* Premium version (value \$40) and Wi-Fi Nokia Body+ scale (\$100). Participants randomized to the MT group will receive *Lose-It* Basic version (free) plus a \$25 stipend for their participation in each assessment point (3). The men will be randomly assigned to the intervention and comparison groups as they are enrolled using an allocation schedule created by the project statistician. The research nurses will not be blinded to the group assignment as they must conduct the app download on the subject's phone and conduct orientation training of the app with the subject that is specific to their assignment (basic app vs. premium app). Randomization will be predetermined using a random number generator and urn randomization to ensure equal sample sizes.

A comparison group (MT) (n=40) of men will receive the *Lose-It* Basic app. The basic app permits daily self-monitoring of eating and physical activity and manual logging of daily weight. MT participants will be asked at baseline to self-monitor their eating, activity, and weight daily. They will receive no text message prompts for self-monitoring, self-monitoring trend reports, or peer interaction via group. MT participants will complete assessments at baseline, 3 and 6 months postbaseline. MT participants will only receive text message reminders for their assessment visit appointment times.

Description of the Intervention Group (MT+). *Lose-It* Premium permits enhanced customization of goal setting, app automated self-monitoring reminders, customized email reports that outline self-monitoring trends important in supporting motivation and confidence during periods of behavioral action. The Nokia Wi-Fi scale will provide automated coaching, rewards and recording of weight synced to the *Lose-It* app permitting immediate feedback and visual maps of weight trends.

Research Staff Support-Reminder Prompts: MT+ participants will have research staff support available via phone. They will also receive reminder prompts for self-monitoring via text and phone when non-adherence with self-monitoring of dietary intake, physical activity or weight is incomplete for 5 days of greater.

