retention. STUDENTS- log of community outreach activities, implementation time, and outcome, Questionnaire evaluating perceived community outreach skill (identify, engage, evaluate, leadership) administered pre-post clinical rotation, GA/Honors students activity log, dissemination events.

After providing informed consent, the men will be oriented to the ActiGraph GT9X by the research nurse. The men will be instructed to wear the ActiGraph GT9X on their right hip continuously for seven days^{5,6,7}, only removing the device for bathing. Subjects will also be provided with written instructions for device use in addition to the hands-on demonstration, a troubleshooting number, an activity questionnaire to capture recreational and vocational activity, and postage-paid return envelope. After wearing the device for seven days, the men will mail the device back to the UNO investigators, Drs. [name] and [name]. Those men who return the device as indicated will be issued/mailed a \$25.00 incentive for their participation. Phone and text reminders will be sent to subjects on the eighth day (the day after completing the 7-day testing) reminding them to return their ActiGraph by our GA. Those men not returning the Actigraph after the phone and text reminder will be sent a mailed letter encouraging them to return the device with a reminder that failure to return the device will result in no incentive received for their participation.

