Analysis: Accelerometers that contain a minimum of five 10-hour days, including both weekday and weekend days, of tracking will be eligible for analysis^{7, 8}. Our collaborating investigators-UNO biomechanical engineer, [name], and Information Science and Technology Specialist, [name], will supervise the advanced analyses of our ActiGraph data with their UNO graduate students across four forms: 1) Traditional ActiGraph analysis (raw accelerations and step counts per 15 second bouts, 2) Custom bout and sedentary analysis, 3) Nonlinear activity pattern analysis, and 4) Applying deep-learning and advanced analytics^{5,9}. Subjects who participate in this sub-study will be mailed a single-page, individualized, easy to read, plain language, graph report containing their peak activity and sedentary times, as well as a report of minutes of minimum, moderate, and vigorous physical activity from their 7-day measurement period. Subjects will be given the same troubleshooting number to call if they have any questions regarding interpreting this individualized physical activity report.

Statistical Analysis

Descriptive statistics will be calculated on all variables, including frequencies and percentages for recruitment/retention, demographic, and categorical variables. Means and standard deviations will be calculated for all continuous variables and measures at each time point. Feasibility and acceptability analyses for aim 1 are largely descriptive, as we will be assessing participation rates and percentages of eligible men and which were the more effective recruitment methods. Qualitative content analysis, as described by Hsieh and Shannon (110) will guide interpretation of the focus group findings from the intervention participant groups. The interview transcript, reflective memos and observation notes taken during each focus group will

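### Sub-study men in either arm can be mailed a personal activity report before their later outcome visits, because the plan sets no mailing time (minor)

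*Combined protocol and SAP*

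**What the plan says.** The document is the combined protocol and SAP.

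- **Who enters, and when.** Accrual, Feasibility Substudy: "We would like to recruit 15 men, newly joining and currently enrolled in our weight loss trial, via convenience sampling". They are "asked in the calendar order they present for their baseline, 3-month, or 6-month assessment visit". The three visits are named again: "The men will be invited to participate in this sub-study during their regularly scheduled baseline, 3 month, or 6-month assessment visit".
- **No limit by arm.** The one sub-study exclusion, under Exclusion Criteria, is "Substudy exclusion criteria would include a man not currently enrolled" in the trial. The Accrual text mentions both arms: "Both arms in our clinical trial receive the same education/instruction about physical activity". That MT men may join is inferred from this open eligibility; it is not stated outright.
- **What happens next.** Methods, sub-study procedure after the measures table: "After wearing the device for seven days, the men will mail the device back". The Analysis paragraph that follows adds: "Subjects who participate in this sub-study will be mailed a single-page, individualized, easy to read, plain language, graph report". The report shows times of peak activity and of sedentary behaviour, and minutes at each intensity. A telephone number is offered for help in reading it. No mailing date is given.
- **What MT men do not get.** Methods, comparison group: "They will receive no text message prompts for self-monitoring, self-monitoring trend reports, or peer interaction via group". They do log activity in the basic app.
- **What is measured later.** Weight (primary) and self-reported physical activity (secondary) are assessed at baseline, 3 and 6 months. The aim 2 text under Statistical Analysis does not mention sub-study participation.

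**The concern.** The main trial compares two packages of self-monitoring support. The Background treats feedback that lets a man evaluate himself as one of the behavioural factors behind weight-loss success. A personal page on activity and sedentary time is feedback of that general kind. It is assigned to neither arm by the design, it goes to a convenience subset, and it can arrive mid-trial.

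Two things could follow. If recipients fall unevenly between the arms, any effect of the page shifts the between-arm contrast. If the page does more for MT men, who get no other trend report, the contrast narrows even when recipients are evenly split. The outcome most open to this is self-reported physical activity, because the page tells a man how many minutes he spends at each intensity. An effect on weight is less plausible. The pilot is meant to supply effect-size estimates for a later trial, so an avoidable co-intervention is worth removing if that is cheap.

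**Working it through.** **1. Who can be exposed.** The men are followed for 26 weeks, so month 3 falls at about week 13. A baseline entrant finishes wearing the sensor at week 1, about 12 weeks before his 3-month visit. The turnaround for the report is not stated.

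| Entry visit | Report can precede 3-month outcome | Report can precede 6-month outcome |
|---|---|---|
| Baseline | yes | yes |
| Month 3 | no | yes |
| Month 6 | no | no |

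The split by entry visit is not given. The ceiling is 15/80 = 18.8% of men. If two thirds enter before month 6 (assumption), 10 are exposed.

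**2. The plan's own figure, for scale.** This point rests on no stated number, but Accrual gives 164 men for 80% power on the time-by-group interaction (f = 0.10, alpha 0.05, 3 time points, correlation 0.5). With noncentrality f² × N × 3/(1 − 0.5) and degrees of freedom 2 and 2(N − 2), N = 164 gives noncentrality 0.01 × 164 × 3/0.5 = 9.84 and power 80.5%. The stated figure is reproduced. At N = 80 the noncentrality is 4.8 and power is 47.9%.

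**3. Chance imbalance.** Assume visit order is unrelated to arm. With n exposed men, the number x in MT is hypergeometric: P(x) = C(40, x) × C(40, n − x)/C(80, n). The arms differ by D = |2x − n| recipients.

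| Exposed n | P(D ≥ 5) | P(D ≥ 7) | Expected D | Expected D/40 |
|---|---|---|---|---|
| 15 (ceiling) | 0.252 | 0.083 | 2.85 | 0.071 |
| 10 (assumption) | 0.087 | 0.014 | 2.30 | 0.058 |
| 8 (assumption) | 0.057 | 0.005 | 2.08 | 0.052 |

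For even n, D is even, so D ≥ 5 means D ≥ 6. At the ceiling, MT is expected to hold 7.5 of the 15, with a 95% range of 4 to 11.

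**4. Effect on the contrast.** Let the page change the outcome by e₊ in an MT+ recipient and by e₀ in an MT recipient. With x₊ and x₀ recipients, the contrast shifts by (x₊e₊ − x₀e₀)/40.

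- Equal effects (e₊ = e₀ = e): the shift is (x₊ − x₀)e/40. It is zero on average, and its expected size is 0.05e to 0.07e from the table.
- Even split, unequal effects: the shift is (n/2)(e₊ − e₀)/40. That is 7.5/40 = 0.19 of the difference in effects at the ceiling, and 5/40 = 0.125 with 10 exposed.

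**5. An unfavourable case for dilution.** Suppose the page does nothing in MT+ and gives an MT recipient a share g of the whole MT+ effect (g is an assumption). The contrast shrinks by (MT recipients/40) × g.

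| g | 7.5 MT men exposed | Power at N = 80 | 5 MT men exposed | Power at N = 80 |
|---|---|---|---|---|
| 0.10 | 1.9% | 46.3% | 1.3% | 46.8% |
| 0.25 | 4.7% | 44.1% | 3.1% | 45.3% |
| 0.50 | 9.4% | 40.3% | 6.3% | 42.8% |

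The starting point is 47.9%.

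**The case against.** The strongest reply is that the plan does not contradict itself. A reader might infer that MT men are handed the very feedback the plan denies them. The documents do not support that. What MT men are denied is the text prompts, the peer group and the trend reports, which in context are the customised e-mail reports of the premium app. One page from a single week of sensor wear is a snapshot, with no diet data, no weight data and no prompts. MT men also already follow their own activity in the basic app, with the same step goal and activity instruction as MT+ men. This stands: the page is similar in kind, but not the same item.

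A reader might also infer that exposure is one-sided and so must dilute the contrast. It need not. MT+ sub-study men receive the same page, and an equal effect cancels on average. This stands too. It leaves chance imbalance, and the possibility that the page adds more for men who receive no other trend report.

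A third point concerns size. The 25% and 8% chances of a gap of at least 5 or 7 recipients assume that all 15 men are exposed, yet 6-month entrants cannot be. A gap of 5 (5/40 = 0.13 of the effect on a recipient) is a tail case. The expected gap is about half that.

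The statement that both arms receive the same activity instruction does not answer the point, since it concerns teaching given to everyone and not a page sent later to a subset.

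**Conclusion.** The point holds as a minor one. As written, the procedure lets men of either arm receive an individual activity report before their own 3- or 6-month outcomes, with no hold on mailing and no balance by arm. At most 15 of 80 men are exposed, and fewer if some enter at month 6. The expected gap between arms is 2 to 3 recipients, or about 0.05 to 0.07 of the report's effect on a recipient.

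This rests on three assumptions: visit order is unrelated to arm; any dropout is similar in recipients and other men, so that the fractions of 40 per arm carry over; and reports come back quickly enough to precede a later visit. The effect of one report is unknown, and the documents give no evidence on its size. Nothing here shows that the weight result would be materially biased.

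**What to change.** In the sub-study Analysis paragraph, state that the individual report is mailed only after the man's 6-month assessment. In the sub-study procedure, require that arm and entry visit be recorded for each participant. With the hold in place, no man has a report before an outcome visit, and the sub-study loses no data.

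If any reports have already gone out before an outcome visit, record the dates and repeat the aim 2 activity and weight analyses without those men. Label this a descriptive sensitivity check: it could remove up to 15 of 80 men from a comparison with about 48% power for its own assumed effect, so a changed p-value would mean little. Compare the estimates and intervals instead.

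The cost is one or two sentences, two recorded items per sub-study man, and a wait of up to six months for men who enter at baseline.

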A total of 8-10 community advisory board members (CAB), 42 student nurses from the UNMC Northern Division NRSG 413 Population Centered Care course, and 80 rural male subjects (40 per group) are needed to achieve the proposed objectives. The sample will consist of 80 men (40/group) who meet the inclusion criteria. Hertzog 74suggested that 30 participants per group in a pilot study is a sufficient sample size for aims involving between group differences and if the results are to be used to estimate the needed sample size for a future, fully- powered study. It is important for this study that we obtain reliable estimates of effect size with which to perform a power analysis for subsequent research, so 40 participants per group will be sought, for a total of 80. Some participants will likely not complete the study, so we will enroll 80 men to allow for up to a 30% attrition rate. Power for the repeated measures analysis of variance (RM-ANOVA) was determined using G*Power 3.1.9. A within-between interaction will be the primary test of significance (time*group interaction). Assuming a small effect size ($f=.10$),⁷⁵ a significance level of .05, 3 time points, and an estimate of .5 for the correlation between time points, 164 participants (82 per group) would be needed to have 80% power. Because this is a pilot study, a smaller sample size is justified, and the results of the pilot study will be used to update the power analysis prior to a future study.

Purposeful justification for the total number of community advisory board members and student nurses is based upon their information rich knowledge of the rural context as either community leaders or students in a rural college of nursing. Justification of the total sample size desired for the community advisory board is based upon optimal group function / interaction (8-10 persons) documented in previous advisory board work in agricultural based locales (Kingman, Yoder, Hodge, Ortega, & Field, 2004). Justification for inclusion of 42 student nurses was based upon the aim of the R-15 AREA NIH mechanism to expose undergraduate students to research. Community outreach is a concept taught in NRSG 413- Population Centered Care. It was deemed feasible to involve all students enrolled in this NRSG 413 course to the community outreach activity of this study- without excluding any student.

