Aim #2: Determine preliminary efficacy of a MT+ intervention to a comparison group receiving only a basic self-monitoring app (MT) in achieving 1) weight loss (primary), and 2) improved diet and increased PA (secondary) at 3 months post-baseline and follow-up at 6 months post-baseline in rural men. The efficacy analyses for aim 2 will be tested via RM-ANOVA models, as they provide a direct measure of differences between the intervention and comparison groups in weight loss and dietary and PA behaviors across the study, as well as effect size estimates. Huynh-Feldt corrected F-tests will be used in order to account for any possible violation of sphericity. If there is a higher than expected attrition rate, a maximum likelihood estimation method (e.g. mixed models) will be used instead of RM-ANOVA in order to utilize all available data and not delete cases in a listwise manner. Overall weight lost at follow-up will be assessed via an independent groups t-test. Outcome variables that are not normally distributed will either be transformed or assessed with nonparametric methods.

Aim #3: Determine quantitative and qualitative indicators of community capacity (resource mobilization, learning opportunities-skills development, partnership linkages, participatory decision- making, leadership) to support a relevant weight loss intervention for rural men. For aim 3, multiple indicators of community capacity will be used to evaluate support for the weight loss intervention applying best practice recommendations (113), 1) CAB- assessed community capacity change survey report by CAB, participation level of members (i.e. # meetings, activities, resources allocated, partnership/network linkages, leadership roles assumed), member attrition with reasons, Qualitative indicators of community capacity in CAB include perceived benefits/skills gained, barriers and facilitators of retention, proposed strategies to increase retention, CAB evaluation of student outreach activities, 2) STUDENTS- clinical log of community outreach activities (type, number, hours) developed, implemented, and outcome,

leadership activities (dissemination via honors projects, clinical conference and class presentations). Qualitative indicators of community capacity among students will include perceived skill development, and leadership confidence. Graduate level students help in training sessions, data collection and implementation of intervention.

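### Weight is tested on complete cases unless attrition is higher than expected; even read as 30% per arm, that can drop 24 of 80 men from the primary test, so the mixed model should be unconditional

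*Combined protocol and SAP*

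**What the plan says.** Statistical Analysis, Aim #2, assigns repeated-measures ANOVA (RM-ANOVA) with Huynh-Feldt correction to weight (primary) and to diet and physical activity (secondary). It then gives a conditional replacement: "If there is a higher than expected attrition rate, a maximum likelihood estimation method (e.g. mixed models) will be used instead of RM-ANOVA", the purpose being "in order to utilize all available data and not delete cases in a listwise manner". A second weight analysis follows: "Overall weight lost at follow-up will be assessed via an independent groups t-test". No missing-data rule is given for that t-test, and no sensitivity analysis for missing weights is described.

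Accrual names the time-by-group interaction as the primary test. On numbers it says "we will enroll 80 men to allow for up to a 30% attrition rate", and it cites a source for the view that "30 participants per group in a pilot study is a sufficient sample size". Methods (Intervention) also describes 30% oversampling in each group, based on average attrition rates. It places randomisation after the baseline visit, so every randomised man should have a baseline weight.

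**The concern.** The reason given for switching method is that RM-ANOVA discards men with incomplete data. That is equally true at 10% or 25% attrition, yet below the threshold the plan accepts the loss. A man who attends at baseline and 3 months and then leaves contributes nothing to the primary test. A man who misses only month 3 has not left the study, but he is deleted too. The t-test keeps the second man and drops the first.

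Two things are at stake. The certain one is precision: Accrual says the pilot must give reliable effect sizes for planning the next trial. The conditional one is bias, if the men who drop out differ in weight response and do so differently by arm. Methods treats the arms differently in ways that could affect attendance (a stipend per assessment is stated for MT, staff prompts for MT+). Equal dropout should therefore not be assumed, though the direction is unknown.

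**Working it through.** **1. The plan's own figure.** Accrual uses f = 0.10, alpha 0.05 and three visits. Its remaining input and its result read: "an estimate of .5 for the correlation between time points, 164 participants (82 per group) would be needed to have 80% power". For the within-between interaction with two groups, the noncentrality is λ = f² × N × 3/(1 − 0.5), with df 2 and 2(N − 2).

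| N | λ | Power |
|---|---|---|
| 164 | 0.01 × 164 × 6 = 9.84 | 80.5% |
| 80 (no loss) | 4.80 | 47.9% |
| 56 (30% lost) | 3.36 | 34.7% |

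N = 162 gives 79.98%, so 164 is reproduced.

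**2. How many men can be dropped.** 30% of 40 is 12 per arm, or 24 of 80, leaving 28 per arm. A rate of exactly 30% is not higher than 30%, so the switch would not apply. If oversampling by 30% instead means 1.3 times the number needed, the allowance is 80 − 80/1.3 ≈ 18 men. In addition, if 5–10% of the 56 missed only month 3 (an assumption), RM-ANOVA would keep 50–53 men, with power 31–33%.

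**3. What the likelihood model recovers at 30% random loss.** I used generalised least squares with equal variances and correlation 0.5, 28 complete men per arm, and 12 lost men per arm who have a baseline weight and, for all or half of them, a month-3 weight. The complete-case standard error of the arm difference in change is √(2/28) = 0.267 SD at either visit.

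| Lost men seen at month 3 | SE, 6 months | SE, 3 months | Power |
|---|---|---|---|
| All 12 per arm | 0.254 (5.2% smaller) | 0.224 (16% smaller) | 39–45% |
| 6 of 12 per arm | 0.255 (4.6% smaller) | 0.238 (11% smaller) | 38–42% |

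The power ranges run from an effect that grows linearly to one that is full by month 3. They use the completers' df and are approximate. If none of the lost men were seen at month 3, both standard errors would be about 4% smaller and power 37–38%.

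**4. Bias.** The documents give no SD or dropout pattern, so these inputs are assumed: no true effect; SD of change 4 kg at 3 months and 5.5 kg at 6 months; correlation between changes 0.5–0.8; odds of dropout 2–3 per SD of smaller 3-month loss; all dropout after month 3. I simulated 1,000,000 men per arm, using only splits with neither arm above 30%. The entries are the false 6-month difference among completers, in favour of the arm with more dropout.

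| Dropout | corr 0.5, odds 2 | 0.5, odds 3 | 0.8, odds 2 | 0.8, odds 3 |
|---|---|---|---|---|
| 30% vs 20% | 0.19 kg | 0.24 | 0.28 | 0.37 |
| 30% vs 10% | 0.33 kg | 0.48 | 0.54 | 0.74 |

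A separate run put the top of the two ranges at 0.39 and 0.77 kg, so about 0.2–0.4 and 0.3–0.8 kg. For scale, the complete-case standard errors are 5.5 × √(1/28 + 1/32) = 1.42 kg and 5.5 × √(1/28 + 1/36) = 1.39 kg. The likelihood estimate was within about 0.02 kg of zero throughout.

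With 30% lost in each arm under the same mechanism, the complete-case difference was also about zero. With 30% in each arm but random dropout in MT and dropout related to poor 3-month loss in MT+ (log-odds 0.5–1.0 per SD), completers favoured MT+ by 0.14–0.25 SD of change at 3 months and 0.07–0.13 SD at 6 months.

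**The case against.** The strongest reply is that the plan already sees the problem. It names the remedy, and the Aim 1 measures table has retention monitored weekly. The only attrition figure in the documents is 30%. Methods applies it to each group and bases it on average rates, so the threshold is less vague than it looks. This stands. A reader might infer that the trigger has no meaning, or that a split such as 40% against 20% would escape it because the overall rate is 30%. The documents do not support that. On the natural per-group reading, one arm exceeds 30% and the likelihood model applies. What remains open is a missing cross-reference and an unnamed visit.

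The second reply is that the harm is small and the trial is a pilot that openly accepts low power. The 6-month gain is indeed modest. But accepting low power for want of men does not justify discarding weights already measured, and the same section asks for reliable effect sizes.

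The third reply is that a mixed model in a small sample can be anti-conservative. This also stands. With 40 per arm, no effect and 30% random loss (3,000 simulated trials), maximum likelihood with a chi-square Wald test rejected in 6.8–7.2% of trials, and an F reference with completers' df in 5.9–6.4%. The estimation and df method must therefore be stated.

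A last reply is that stating the trigger as 30% in either group at a named visit would be a smaller edit. It would settle the ambiguity but recover no data below that rate.

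**Conclusion.** The concern holds in a limited form. The default primary analysis is complete-case and can omit up to 24 of 80 men, 12 per arm, on the plan's most natural reading of its own threshold. The sure cost is precision: 35% power against about 38–45%, and standard errors about 5% smaller at 6 months and 11–16% smaller at 3 months with the likelihood model. These figures assume the plan's inputs, 30% random loss, and half or all of the lost men seen at month 3.

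A reader might also infer that the trial's result will be biased, or biased towards MT+. The documents do not show this. Bias needs dropout related to observed weight, with a rate or a mechanism that differs by arm. Nor does equal attrition guarantee safety, because equal rates are unbiased only if the mechanism is also the same in both arms. The kilogram figures rest on assumed inputs, and the protection offered by the likelihood model assumes data missing at random. Severity: lower end of should-fix.

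**What to change.** Delete the attrition condition in Statistical Analysis, Aim #2, and replace it with wording such as:

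> Weight will be analysed with a linear mixed model with arm, visit and arm-by-visit terms and an unstructured covariance over the three visits, fitted by REML with Kenward-Roger (or similar small-sample) degrees of freedom. Every randomised man is included in his assigned arm with all his available weights, whatever the attrition rate. The arm-by-visit test is the primary test. The 6-month arm difference in weight change, with its 95% CI, is taken from this model. RM-ANOVA on men with all three visits and the independent-groups t-test are sensitivity analyses. The number of men with each pattern of attended visits is reported by arm.

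The existing rule for non-normal outcomes ("Outcome variables that are not normally distributed will either be transformed or assessed with nonparametric methods") can stay.

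The cost is SAP wording and slightly more analysis work, with no new data, visits or participants. One limit should be stated: if dropout depends on the unseen 6-month weight, the mixed model does not remove the bias. A missing-not-at-random sensitivity analysis, with its values fixed before outcomes are compared by arm, is an optional addition.
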